### 10.6.11Treatment Compliance

Each dose of IMP will be taken under supervision and a hand and mouth check conducted. The exact dosing time for each subject will be recorded on the subject's CRF.

## 10.7 Efficacy and Safety Variables

### **10.7.1 Flow Chart**

A schedule of study assessments is provided in Table 6, Table 7 and Table 8.

Simbec-Orion personnel who have been appropriately trained will carry out study procedures.

Where more than 1 procedure is scheduled for the same time-point, the following order of priority will apply:

- 1. PK and PD blood sampling. Blood samples collected outside of the defined deviation windows will be recorded as protocol deviations. The allowable window is  $\pm$  1 minute for samples collected up to 30 minutes time-point (inclusive) and  $\pm$  5 minutes for samples collected > 30 minutes time-point.
- 2. Holter extraction resting time. Start of resting time will be recorded.
- 3. Vital signs and 12-lead ECG (a window of  $\pm$  15 min in relation to the nominal time-point is allowed).
- 4. Start or finish of urine collection interval (a window of  $\pm$  10 min in relation to the nominal time-point).
- 5. All pre-dose assessments may be performed within the 1 h before dosing, except pre-dose urine samples can be collected outside this window.

As guidance, where Holter extracted ECGs coincide with other procedures *i.e.* vital signs and ECGs the order of procedures will be:

[figure not shown]
Confidential

RD 777/34920 DNDi- 0690- 02

**DNDi** 

Final V3.0/ Date 07 December 2020

Page 65 of 109

ECGs and Holter extractions should be taken prior to vital signs when both measurements are scheduled at the same time point. Holter extracted ECGs will be taken in the 10 min immediately prior to the nominal PK time point (window -10 to -3 minutes prior to PK timepoint) and no other procedures will be performed within this time window. Vital signs shall be taken prior to PK sampling. Other assessments, *i.e.* physical examinations etc, will be performed after PK sampling within the required time windows.

All safety assessments will be timed and performed relative to the start of dosing.

Confidential

Final V3.0/ Date 07 December 2020

Page 66 of 109

**Table 6 Study Flow Chart: Part A** 

**DND**i

RD 777/34920

DNDi- 0690- 02

			Resident in the Clinical Unit													
	Screening	Admissio						IMP I	Dosing I	Period					Discharge	Post Study Follow-up
		n														
Study Day	D-28 to	D-2	D-1	D1	D2	D3	D4	D5	D6	D7	D8	D9	D10	D11	D12	D24-D28
	D-3														(last dosing +2 days)	(last dosing + 14-18 days)
General Assessments	S															
Informed consent	X															
Medical and surgical history	X															
Demographic Data	X															
Hepatitis/HIV	X															
serology																
PCR test COVID- 19		X														
Inclusion/Exclusion criteria 	X	X		X	X	X	X	X	X	X	X	X	X			
Weight and height	X														X (Weight only)	
Vein assessment	X															
Urine drugs of abuse and alcohol/cotinine screen	X	X														
Randomisation				X	•											
IMP administration				X	X	X	X	X	X	X	X	X	X			

# Clinical Study Protocol

Confidential

Final V3.0/ Date 07 December 2020

Page 67 of 109

		Resident in the Clinical Unit														
	Screening	Admission			IMP Dosing Period								Discharge	Post Study Follow-up		
Study Day	D-28 to D-3	D-2	D-1	D1	D2	D3	D4	D5	D6	D7	D8	D9	D10	D11	D12 (last dosing +2 days)	D24-D28 (last dosing + 14-18 days)
Safety Assessments																
Physical examination 	X (Full)	X (Brief)					X (Brief)			X (Brief)					X (Brief)	X (Brief)
Laboratory safety tests (biochemistry,	X	X			X		X			X			X		X	X
haematology, coagulation, urinalysis and urine microscopy) 																
Troponin I 		X											X			
FSH (post-menopausal female subjects only)	X															
Holter monitoring (for extraction of ECGs) 			X										X			
12-lead ECG 	X	X		X			X			X			X		X	
Vital signs 	X	X		X			X		_	X			X	_	X	X
Adverse events	X	X	X	X	X	X	X	X	X	X	X	X	X	X	X	X
Serious adverse events	X	X	X	X	X	X	X	X	X	X	X	X	X	X	X	X
Prior and concomitant medication	X	X	X	X	X	X	X	X	X	X	X	X	X	X	X	X

### Clinical Study Protocol

Confidential

Final V3.0/ Date 07 December 2020

Page 68 of 109

								Re	sident i	n the Cl	inical L	nit				
	Screening	Admission			IMP Dosing Period										Discharge	Post Study Follow-up
Study Day	D-28 to D-3	D-2	D-1	D1	D2	D3	D4	D5	D6	D7	D8	D9	D10	D11	D12 (last dosing +2 days)	D24-D28 (last dosing + 14-18 days)
Pharmacokinetic	Assessments															
Plasma samples for DNDI-0690 and metabolite 				X	X	X	X	X	X	X	X	X	X	X	X	
DBS samples for DNDI-06909				X									X	X	X	
Urine samples for DNDI-0690 				X			X			X			X			
Other assessment	s															
Urine samples for exploratory biomarkers 				X	X		X			X			X			
Full blood sampling for transcriptional profiling (mRNA) assessment (Part A Cohorts 2 & 3 only) 		X											X			

#### **Study Flow Chart Footnotes:**

- 1. Full inclusion/exclusion criteria will be checked at Screening. Eligibility will be re-confirmed on Day -2 and prior to each dose administration.
- 2. Physical examination: Full physical examination will be performed at Screening. A brief physical examination will be performed on Day -2, Day 4, Day 7, Day 12 and Post Study follow-up.
- 3. Laboratory safety tests will be performed at Screening, Day -2, pre-morning dose on Day 2/Day 4/Day 7/Day 10, Day 12 and Post Study follow-up. Glomerular Filtration Rate (GFR) will be estimated at Screening for eligibility purposes and at each time point, using the CKD-EPI equation. GFR based on Cys C results (GFRcc) will also be assessed.
- 4. Troponin I sample will be taken at Day -2 and Day 10 (pre--morning dose)
- 5. Holter monitoring will begin 60 minutes prior to the theoretical Day 1 morning dosing time on Day -1 and begin approximately 60 minutes prior to dosing on Day 10. Holter monitoring will end any time after Day 1 morning dosing and end any time after Day 11 (24 h post-last dose) PK sample collection. One set of triplicate ECG extractions to be taken at pre-morning dose (for baseline; T-30min to T-15 min) and at 0.5, 1, 2, 3, 3.5, 4, 6, 9, 12 and 24 h post-morning dose, time-matched on Day 10 timepoints for the Day -1 timepoints. Extractions are always done within the 10 minutes prior to PK sampling, except at pre-dose.

Confidential

RD 777/34920 DNDi- 0690- 02

**DNDi** 

Final V3.0/ Date 07 December 2020

Page 69 of 109

- 6. 12-lead ECGs will be taken at Screening, Day -2, Day 1/Day 4/Day 7/Day 10 (pre-morning dose and 4 h post-morning dose) and Day 12. Day 1, pre-morning dose ECG will be taken in triplicate (for baseline), all post-dose time points will be single ECG. An ECG can be repeated for any reason (technical in particular).
- 7. Vital signs (supine blood pressure, heart rate and Tympanic temperature) will be measured at Screening, Day -2, pre-morning dose on Day 1/Day 4/Day 7/Day 10, Day 12 and Post Study follow-up.
- 8. Plasma samples for DNDI-0690 and metabolite will be taken (4 mL K2EDTA tube) on Day 1 (pre-morning dose and 0.5, 1, 2, 3, 3.5, 4, 6, 9, 12 h post-morning dose), pre-morning dose on Day 2-Day 9 and Day 10 (pre-last dose and 0.5, 1, 2, 3, 3.5, 4, 6, 9, 12 h post-last dose).
- 9. Dried blood spot (DBS) samples for DNDI-0690 will be taken (2 mL K2EDTA vacuum tube) on Day 1 (pre-morning dose, 0.5, 1 and 2 h post morning dose) and Day 10 (pre-last dose and 0.5, 1, 2, 3, 3.5, 4, 6, 9, 12 h post-last dose), Day 11 (24 h post-last dose) and Day 12 (48 h post-last dose).
- 10. Urine samples for DNDI-0690 will be collected on Day 1 (pre-morning dose and 0-24h post-morning dose) and on Day 4/Day 7/Day 10 (0-24 h post-morning doses).
- 11. Urine samples for exploratory biomarkers (Cys C, Kidney Injury Molecule-1 (KIM-1) and Neutrophil Gelatinase-Associated Lipocalin (NGAL)) will be collected at pre-morning dose on Day 1/Day 2/Day 4/Day 7/Day 10 (from morning spot collection).
- 12. Full blood sampling for transcriptional profiling (mRNA) assessment (Part A Cohorts 2 & 3 only) will be collected (2.5 mL vacutainer PAXgene® blood RNA tube) on Day -2 and Day 10 (pre-morning dose).

Clinical Study Protocol

Final V3.0/ Date 07 December 2020

Page 70 of 109

Confidential

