#### Day 4 and Day 7:

- o Eligibility check: Pre-dose
- Dosing
- A brief physical examination
- Laboratory safety tests (biochemistry, haematology, coagulation, urinalysis, urine microscopy): Pre-morning dose
- o 12-lead ECG: Pre-morning dose and 4 h post-morning dose
- Vital signs (supine systolic and diastolic blood pressure, pulse rate, and tympanic temperature)
- o AE
- o SAE
- Prior and concomitant medication
- o PK plasma sample for DNDI-0690 and metabolite: Pre-morning dose
- O PK urine samples for DNDI-0690:[0-24] h post-morning dose
- o Urine samples for exploratory biomarkers: Pre-morning dose

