Following single oral administration of DNDI-0690 in capsule form in the fasted state over the 10 mg to 3600 mg dose range, exposure to DNDI-0690 increased in a sub-proportional manner based on  $C_{max}$ ,  $AUC_{last}$  and  $AUC_{0-inf}$ .

[figure not shown]
Final V3.0/ Date 07 December 2020

Confidential

Page 42 of 109

DNDi RD 777/34920 DNDi- 0690- 02

Figure 4 Geometric Mean (×/÷ Geometric SD) Plasma DNDI-0690 Concentrations (ng/mL) Following Single Oral Doses of 10, 30, 150, 400, 1200 and 3600 mg in Healthy Males in the Fasted State: Pharmacokinetic Population

Peak and overall exposure levels of DNDI-0690 were increased (between 67% and 75%) in the fed state (400 mg dose level) when compared to the fasted state. These increases were statistically significant for  $C_{max}$  but not for AUC due to the higher between subject variability seen in the overall exposure levels.

Plasma exposure ( $C_{max}$  and AUC) of DNDI-0690 was statistically significantly increased when dosed in female subjects compared with male subjects (at same 1200 mg dose level). When normalized by weight, plasma exposure was still higher in female subjects than in male subjects, but the difference was no longer statistically significant (between 12% and 33% higher on average).

Following single oral administration of DNDI-0690 in capsule form at doses ranging from 10 mg to 3600 mg, DNDI-0690 was absorbed with median  $T_{max}$  occurring between 1.500 h and 4.000 h post-dose with no impact of food or gender.

Over the 10 to 3600 mg range, DNDI-0690 concentrations declined in a monophasic or biphasic manner with resultant geometric mean half-life ranging from 4.547 to 12.144 h across all regimens, with no impact of food or gender. The proportion of DNDI-0690 eliminated via renal route was low across all regimen with mean cumulative urine Fe (%) values over 72 hours of between 0.00350% and 0.0220%.

The inter-subject variability associated with exposure was low to moderate over the 10 mg to 3600 mg dose range with no impact of food, however, variability appeared lower in females compared to males.

At the highest dose level of 3600 mg DNDI-0690, the maximum values of  $C_{max}$  and  $AUC_{0-24}$  in individual subjects were 3160 ng/mL and 42,600 ng.h/mL respectively. These values were

DNDi RD 777/34920 DNDi- 0690- 02

Final V3.0/ Date 07 December 2020

Confidential

Page 43 of 109

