#### **Study Flow Chart Footnotes:**

- 1. Full inclusion/exclusion criteria will be checked at Screening. Eligibility will be re-confirmed on Day -2 and prior to each dose administration.
- 2. Physical examination: Full physical examination will be performed at Screening. A brief physical examination will be performed on Day -2, Day 4, Day 7 and Post Study follow-up.
- 3. Laboratory safety tests will be performed at Screening, Day -2, pre-dose on Day 2/Day 4/Day 5, Day 7 and Post Study follow-up. Glomerular Filtration Rate (GFR) will be estimated at Screening for eligibility purposes and at each time point, using the CKD-EPI equation. GFR based on Cys C results (GFRcc) will also be assessed.
- 4. Troponin I sample will be taken at Day -2 and Day 5 (Pre-dose).
- 5. Holter monitoring will begin 60 minutes prior to the theoretical Day 1 dosing time on Day -1 and begin approximately 60 minutes prior to dosing on Day 5. Holter recording will end any time after Day 1 dosing and end any time after Day 6 (24 h) post-last dose PK sample collection. One set of triplicate ECG extractions to be taken at pre-dose (for baseline; T-30min to T-15 min) and at 0.5, 1, 2, 3, 3.5, 4, 6, 9, 12 and 24 h post-dose, time-matched on Day 5 timepoints for the Day-1 timepoints. Extractions are always done within the 10 minutes prior to PK sampling, except at pre-dose.
- 6. 12-lead ECGs will be taken at Screening, Day -2, Day 1/Day4/Day 5 (pre-each dose and 4 h post-dose) and Day 7. Day 1, pre-dose ECG will be taken in triplicate (for baseline), all post-dose time points will be single ECG. An ECG can be repeated for any reason (technical in particular).
- 7. Vital signs (supine blood pressure, heart rate and Tympanic temperature) will be measured at Screening, Day -2, pre-dose on Day 1/Day 4/Day 5, Day 7 and Post Study follow-up.
- 8. Plasma samples for DNDI-0690 and metabolite will be taken (4 mL K2EDTA tube) on Day 1 (pre-dose and 0.5, 1, 2, 3, 3.5, 4, 6, 9, 12 h post-dose), pre-dose on Day 2/Day 3/Day 4 and Day 5 (pre-dose and 0.5, 1, 2, 3, 3.5, 4, 6, 9, 12 h post-dose), Day 6 (24h post-last dose) and Day 7 (48h post-last dose).
- 9. Dried blood spot (DBS) samples for DNDI-0690 will be taken (2 mL K2EDTA vacuum tube) on Day 1 (pre-dose, 0.5, 1 and 2 h post-dose) and Day 5 (pre-dose and 0.5, 1, 2, 3, 3.5, 4, 6, 9, 12 h post-dose), Day 6 (24 h post-last dose) and Day 7 (48 h post-last dose).

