#### **Study Flow Chart Footnotes:**

- 1. Full inclusion/exclusion criteria will be checked at Screening. Eligibility will be re-confirmed on Day -2 and prior to each dose administration.
- 2. Iohexol administration: All subjects will receive 5 mL of iohexol solution (300 mg/mL iodine) intravenously on Day -1, Day 10, and optionally on Day 24-28 (Post Study follow-up) that will be flushed with 10 mL of normal saline solution. On Day -1, iohexol solution will be administered at the same time as expected dosing of the study drug or placebo on Day 10. On Day 10, iohexol solution will be administered immediately after dosing of study drug or placebo.
- 3. Physical examination: Full physical examination will be performed at Screening. A brief physical examination will be performed on Day -2, Day -1, Day 4, Day 7, Day 12 and Post Study follow-up.
- 4. Laboratory safety tests will be performed at Screening, Day -2, pre-morning dose on Day 2/ Day 4/Day 7/Day 10, Day 12 and Post Study follow-up. Glomerular Filtration Rate (GFR) will be estimated at Screening for eligibility purposes and at each time point, using the CKD-EPI equation. GFR based on Cys C results (GFRcc) will also be assessed.
- 5. Troponin I samples will be taken on Day -2, Day 1 (pre-morning dose) and Day 10 (Pre-last dose).
- 6. 12-lead ECGs will be taken at Screening, Day -2, Day -1 (pre-iohexol dose), Day 1/Day 4/Day 7/Day 10 (pre-morning dose and 4 h post-morning dose) and Day 12. Day 1, pre-morning dose ECG will be taken in triplicate (for baseline), all post-dose time points will be single ECG. An ECG can be repeated for any reason (technical in particular).
- 7. Vital signs (supine blood pressure, heart rate and Tympanic temperature) will be measured at Screening, Day -2, Day -1 (pre-iohexol dose), pre-morning dose on Day 1/Day 4/Day 7/Day 10, Day 12 and Post Study follow-up.
- 8. Plasma samples for DNDI-0690 and metabolite will be taken (4 mL K2EDTA tube) at pre-morning dose on Day 1/Day 2/Day 4/Day 7 and Day 10 (pre-last dose and 0.5, 1, 2, 3, 4, 6, and 9 h post-last dose), Day 11 (24h post-last dose) and Day 12 (48h post-last dose).

Clinical Study Protocol

Final V3.0/ Date 07 December 2020

Confidential

Page 75 of 109

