# 10.9.2 Study Variables/Endpoints

#### 10.9.2.1 Primary Endpoints

Safety parameters (changes in vital signs, ECG, safety laboratory parameters with special focus on renal function parameters, *i.e.* serum creatinine, blood urea nitrogen (BUN), and Cys C), and frequency and severity of observed TEAEs.

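### No blood pressure or temperature reading is scheduled near peak drug level in Parts A, B or C, although change in vital signs is a primary endpoint

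*Protocol*

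**What the plan says.** Section 10.9.2.1 defines the primary endpoint as "Safety parameters (changes in vital signs, ECG, safety laboratory parameters with special focus on renal function parameters" and so on, together with treatment-emergent adverse events. Section 10.9.2.5.3 summarises vital signs as absolute values and as change from Day 1 pre-dose. Section 10.2.1 lists vital signs among the safety data reviewed before each escalation.

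The measurement times are in footnote 7 of each flow chart in Section 10.7.1:

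- Part A (Table 6): vital signs "will be measured at Screening, Day -2, pre-morning dose on Day 1/Day 4/Day 7/Day 10, Day 12 and Post Study follow-up".
- Part B (Table 7): they "will be measured at Screening, Day -2, pre-dose on Day 1/Day 4/Day 5, Day 7 and Post Study follow-up".
- Part C (Table 8): after Screening and Day -2, the times are "Day -1 (pre-iohexol dose), pre-morning dose on Day 1/Day 4/Day 7/Day 10, Day 12 and Post Study follow-up".

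The synopsis agrees wherever it gives a time. Its Part A entry for Days 4 and 7 reads "Vital signs (supine systolic and diastolic blood pressure, pulse rate, and tympanic temperature", closes the bracket and states no time; the Part B synopsis takes over the Day 4 entry by cross-reference. Footnote 7 settles both as pre-dose.

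The 12-lead ECG is timed differently. In Part A it is taken on "Day 1/Day 4/Day 7/Day 10 (pre-morning dose and 4 h post-morning dose) and Day 12" (Table 6 footnote 6), and Tables 7 and 8 also carry a 4 h post-dose ECG.

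Section 8.6.1 reports that in the single-dose study median Tmax was "occurring between 1.500 h and 4.000 h post-dose with no impact of food or gender", with "geometric mean half-life ranging from 4.547 to 12.144 h across all regimens".

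**The concern.** A blood pressure or temperature effect that follows the drug's peak and fades within the dosing interval would fall between the scheduled readings. Every reading that enters the change-from-baseline summary during dosing is a trough value compared with a pre-dose baseline, and the discharge reading is close to washout. The same data go to the escalation review, which may take the daily dose to 2400 mg in Part A and 3600 mg in Part B (Sections 10.3.1 and 10.3.2).

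The protocol fixes when the readings are taken, so no analysis plan can recover the missing ones. The protocol also treats the peak as worth sampling for the ECG on the same days, and gives no reason for leaving out blood pressure and temperature.

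**Working it through.** The plan states no figure for exposure at the time of the vital-sign readings, so there is none to reproduce. The check has three steps.

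**1. Count the scheduled readings (footnote 7 of Tables 6 to 8).**

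| Part | After first dose, before follow-up | Within 12 h after a morning dose |
|---|---|---|
| A | 4 (Days 4, 7, 10 pre-dose; Day 12 at 48 h) | 0 |
| B | 3 (Days 4, 5 pre-dose; Day 7 at 48 h) | 0 |
| C | 4 (Days 4, 7, 10 pre-dose; Day 12 at 48 h) | 0 |

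**2. Exposure at those readings.** The inputs are the half-life range of 4.547 to 12.144 h and the median Tmax range of 1.5 to 4.0 h (Section 8.6.1). With BID dosing the evening dose is 10 h after the morning dose (Section 10.5.3.1), so the next pre-morning reading is 24 - 10 = 14 h after the last dose. Assuming mono-exponential decline from the peak:

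fraction of peak left at time t = 2^(-(t - Tmax)/half-life)

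| Reading | 4.547 h, Tmax 1.5 | 4.547 h, Tmax 4.0 | 12.144 h, Tmax 1.5 | 12.144 h, Tmax 4.0 |
|---|---|---|---|---|
| Once daily, pre-dose (t = 24 h) | 0.032 | 0.047 | 0.277 | 0.319 |
| BID, pre-morning (t = 14 h) | 0.149 | 0.218 | 0.490 | 0.565 |
| Discharge (t = 48 h) | 0.001 | 0.001 | 0.070 | 0.081 |
| A reading at t = 4 h | 0.683 | 1.000 | 0.867 | 1.000 |

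For example, the upper once-daily value is 2^(-(24 - 4)/12.144) = 2^(-1.647) = 0.319.

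Pre-dose readings are therefore at about 3% to 32% of peak once daily and about 15% to just over 56% under BID. The discharge reading is at about 0.1% to 8%. A 4 h reading would be at about 68% to 100%.

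**3. Cross-check against Table 4 (Section 10.3.1), once daily.** Dividing predicted steady-state AUC over the dosing interval by single-dose AUC(0-24) gives 13100/11800 = 1.110 at 400 mg, 23600/19700 = 1.198 at 1200 mg and 44900/32800 = 1.369 at 3600 mg, which match the tabulated accumulation ratios of 1.11, 1.20 and 1.37. With R = 1/(1 - exp(-24k)) and an assumed Tmax of 3 h, the trough is exp(-21k) of the peak: about 13%, 21% and 32%. The 3600 mg ratio implies k = 0.0546 per hour, or a half-life of ln 2/0.0546 = 12.7 h. That is slightly above the reported maximum of 12.144 h, so these percentages are approximate. They lie within the once-daily range from step 2.

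**The case against.** The strongest case on the other side has five parts.

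- **The protocol does not contradict itself.** All three flow charts agree, the endpoint makes no claim about peak effect, and the study is exploratory with descriptive safety summaries (Section 10.9.3). This stands: the point is a weak design choice, not an error.
- **Heart rate is covered.** The 4 h ECG records it in all parts. Holter extractions run to 24 h after the last dose in Parts A and B, though Section 10.7.4.8 defers their analysis until development reaches Phase II. A reader might infer that no vital sign at all is observed near peak; that is not so. The gap is blood pressure and temperature.
- **Prior risk looks modest.** The single-dose study to 3600 mg had no clinically significant vital-sign findings (Section 8.6.1), and monkey telemetry showed no cardiovascular or temperature effect up to 350 mg/kg (Section 8.3). This lowers the urgency but does not close the gap. The timing of the single-dose readings is not shown, and the predicted steady-state geometric mean Cmax at 3600 mg (3380 ng/mL, Table 4) exceeds the highest individual single-dose value at that dose (3160 ng/mL, Section 8.6.1).
- **Other safeguards exist.** Escalation also uses adverse events, ECG, laboratory and PK data, and no stopping criterion in Section 10.2.2 uses blood pressure. Subjects are resident under medical supervision, unscheduled readings are possible, and a symptomatic effect would be recorded as an adverse event. A reader might infer that escalation is unsafe; the document does not support that. What remains exposed is a symptom-free effect near peak.
- **Earlier readings may occur.** Inclusion criteria 10 and 11 mention pre-dose values, and Table 6 footnote 1 re-confirms eligibility before each dose, so pre-dose readings before Day 4 are possible. Section 10.7.2.8 mentions re-confirmation only on Day -2. Such readings would still be at trough.

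**Conclusion.** The point holds for blood pressure and temperature in all three parts: no reading is scheduled within 12 h after a morning dose, against a median Tmax of 1.5 to 4 h. The vital-sign part of the primary endpoint can therefore show absence of effect at trough and after washout, and nothing about the peak.

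The percentages rest on mono-exponential decline, whereas Section 8.6.1 says mono- or biphasic. They also use group-level half-life and Tmax from single doses, so individual subjects may fall outside the ranges. A reader might infer that the readings are always taken at one third of peak or less. That holds only for once-daily dosing under these assumptions; under the BID regimen permitted in Part A the fraction may exceed one half.

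The count of readings needs none of these assumptions, and the conclusion rests on it. The document gives no evidence that a peak effect exists, so this is a worthwhile, inexpensive improvement and not a critical fault.

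**What to change.** Reconcile the vital-signs schedule with the primary endpoint. Add a supine blood pressure and temperature reading at the 4 h post-dose 12-lead ECG visit already in the plan (Days 1, 4, 7 and 10 in Parts A and C; Days 1, 4 and 5 in Part B), and include it in the change-from-baseline table. Amend footnote 7 of Tables 6 to 8, and give the untimed Part A Day 4 and Day 7 synopsis entry the time stated in footnote 7.

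The cost is three or four non-invasive readings per subject. With all six cohorts of 9 enrolled, that is 36 x 4 + 9 x 3 + 9 x 4 = 207 readings. Vital signs need 10 minutes supine (Section 10.7.4.5) and a safety ECG 5 minutes at rest (Section 10.7.4.7), so each reading adds about 5 minutes. It must fit around lunch at about 4 h and, on full-profile days, the 4 h PK sample. Section 10.7.1 already sets the order (ECG, then vital signs, then PK), and Section 10.6.4 exempts study procedures from the upright-posture rule.

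If the schedule is left as it is, state in the protocol and the report that the vital-sign summary covers trough exposure only.
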